8.1.2 Reporting period

The reporting period for AEs will commence from the date of consent, (typically Visit 1: screening visit) and will continue until the follow-up visit (Visit 10: Day 168), The reporting period for SAE will commence from the date of consent, (typically Visit 1: screening visit) and will continue until the end of study (Visit 10: Day 168),

SAEs that are judged to be at least possibly related to the IMP must still be reported in an expedited manner irrespective of how long after IMP administration the reaction occurred.

8.1.2.1 Reporting period : Liver related toxicity only

Due to the specifics associated with the expedited reporting requirements (SAE form) associated with liver related toxicity (8.1.1.4) the reporting time window will commence from the date of consent (typically Visit 1:

screening visit) and will continue until the follow-up visit (Visit 10: Day 168) only. Any SAE reports will be followed up until resolution irrespective of duration. All Liver related events will continue to be reported for the duration of the study – only the expedited reporting/use of SAE reporting procedures will be limited to this time window.

8.2 Reporting Procedure

8.2.1 Site

8.2.1.1 Adverse Events

AEs should be reported on an AE Form (and where applicable on an SAE form). An AE form should be completed at each visit and returned to the trials office.

AEs will be reviewed using the common terminology criteria for adverse events (CTCAE), version 4.0 (see appendix 4). Any AEs experienced by the patient but not included in the CTCAE should be graded by an investigator and recorded on the ae form using a scale of (1) mild, (2) moderate or (3) severe. For each sign/symptom, the highest grade observed since the last visit should be recorded.

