2.2 Primary Outcome Measure

Safety and tolerability parameters include: adverse events, serious adverse, clinical laboratory tests, electrocardiograms, and vital signs. Frequency, type and severity of infections.

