8.1.1.3 Infusion Related Reactions

Infusion-related reactions are defined according to the NCI-CTCAE Version 4.0 definition, as follows:

Grade 1: mild, transient reaction, infusion interruption not indicated; intervention not indicated

Grade 2: therapy or infusion interruption indicated but responds promptly to symptomatic treatment (for example, antihistamines, non-steroidal anti-inflammatory drugs [NSAIDS], narcotics, I.V. fluids); prophylactic medications indicated for \leq 24 hours

Grade 3: Prolonged (for example, not rapidly responsive to symptomatic medication and/or brief interruption of infusion); recurrence of symptoms following initial improvement; hospitalisation indicated for clinical sequelae

Grade 4: Life-threatening consequences; urgent intervention indicated consistent with usual medical practice, selected parenteral medications may be utilised as detailed below. Additional treatments, chosen according to clinical symptoms and local standards, may be utilised at investigator discretion.

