8.2.1.2 Serious Adverse Events

For more detailed instructions on SAE reporting refer to the SAE Form Completion Guidelines contained in the relevant section of the ISF.

AEs defined as serious and which require reporting as an SAE should be reported on an SAE Form. When completing the form, the Investigator will be asked to define the causality and the severity of the AE which should be documented using the CTCAE version 4.0.

On becoming aware that a patient has experienced an SAE, the Investigator (or delegate) must complete, date and sign an SAE Form. The form should be faxed together with a SAE Fax Cover Sheet or emailed to the Trials Office using one of the numbers or the email address listed below as soon as possible and no later than 24 hrs after first becoming aware of the event:

To report an SAE by fax, fax the SAE Form with an SAE Fax Cover Sheet to:

[name] (primary number)

[name] (secondary number)

To report an SAE by email, email a scanned copy of the SAE Form to:

[contact]

On receipt the CDAID Trials Office will allocate each SAE a unique reference number. This number will either be transcribed onto the SAE Fax Cover Sheet which will then be faxed back to the site or emailed back to the site as proof of receipt which should be filed with the SAE form in the ISF. If confirmation of receipt is not received within 1 working day please contact the Trials Office. The SAE reference number should be quoted on all correspondence and follow-up reports regarding the SAE. The SAE Fax Cover Sheet completed by the CDAID Trials Office should be filed with the SAE Form in the ISF.

For SAE Forms completed by someone other than the Investigator, the Investigator will be required to countersign the original SAE Form to confirm agreement with the causality and severity assessments. This should

be done as soon as possible but can be done after returning to the Trial Office so as not to delay initial reporting. The form should then be kept in the ISF.

Investigators should also report SAEs to their own Trust in accordance with local practice.

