APPENDIX 2 - DEFINITION OF ADVERSE EVENTS

Adverse Event

Any untoward medical occurrence in a patient or clinical trial subject administered a medicinal product and which does not necessarily have a causal relationship with this treatment.

Comment:

An AE can therefore be any unfavourable and unintended sign (including abnormal laboratory findings), symptom or disease temporally associated with the use of an investigational medicinal product, whether or not related to the investigational medicinal product.

Adverse Reaction

All untoward and unintended responses to an IMP related to any dose administered.

Comment:

An AE judged by either the reporting Investigator or Sponsor as having causal relationship to the IMP qualifies as an AR. The expression reasonable causal relationship means to convey in general that there is evidence or argument to suggest a causal relationship.

Serious Adverse Event

Any untoward medical occurrence or effect that at any dose:

- Results in death
- Is life-threatening*
- Requires hospitalisation** or prolongation of existing inpatients' hospitalisation
- Results in persistent or significant disability or incapacity
- Is a congenital anomaly/birth defect
- Or is otherwise considered medically significant by the Investigator***
 - Other Medically significant events that need to be reported as an SAE include

• Any suspected or definite diagnosis of cytokine release syndrome grade 3 - 5. In order to confirm the case of cytokine release syndrome, an additional blood sample will need to be taken for cytokine assay (e.g. TNF- α , IFNy, IL-6). This information is to be provided as part of the SAE form.

- Is associated with liver injury and impaired liver function defined as:
- ALT > 3xULN and total bilirubin[#] > 2xULN (>35% direct), **or** ALT > 3xULN and INR## > 1.5.

[#] Serum bilirubin fractionation should be performed if testing is available; if unavailable, measure urinary bilirubin via dipstick. If fractionation is unavailable and ALT \geq 3xULN and total bilirubin \geq 2xULN, then the event is still to be reported as an SAE. ^{##} INR testing not required per protocol and the threshold value does not apply to subjects receiving anticoagulants. If INR measurement is obtained, the value is to be recorded on the SAE form.

Comments:

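### The three-level scale for adverse events not listed in CTCAE conflicts with the protocol's CTCAE-only passages and compresses the AE-form grade of an unlisted life-threatening or fatal event

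*Protocol*

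**What the plan says.** Section 8.2.1.1 sets the general rule: "AEs will be reviewed using the common terminology criteria for adverse events (CTCAE), version 4.0 (see appendix 4"). It then makes an exception. An AE that CTCAE does not include is graded by an investigator and "recorded on the ae form using a scale of (1) mild, (2) moderate or (3) severe". The section goes on: "For each sign/symptom, the highest grade observed since the last visit should be recorded". It does not ask the site to mark which scale a grade came from.

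Serious events are recorded twice: "AEs should be reported on an AE Form (and where applicable on an SAE form"). For the SAE form, Section 8.2.1.2 asks the investigator to "define the causality and the severity of the AE which should be documented using the CTCAE version 4.0". It makes no exception for events outside CTCAE.

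Two other places describe the grading. Table 9 (Section 9.1) says the AE form holds a CTCAE version 4.0 grade. Appendix 3 says toxicities are recorded by CTCAE version 4.0. Neither mentions a three-level alternative.

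The protocol uses CTCAE levels above 3 in several places. Section 8.1.1.2 gives a Grade 4 for hypersensitivity. Section 8.1.1.3 describes Grade 4 infusion reactions as "Life-threatening consequences; urgent intervention indicated". Appendix 2 refers to cytokine release syndrome of grades 3 to 5.

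**The concern.** Two scales with different upper ends feed one grade on one form. On the CTCAE scale a 3 means less than life-threatening. On the scale for unlisted events a 3 is the top level, so it covers everything from severe upwards. A reader of a table by grade could not tell which meaning applies.

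The protocol also gives a site two instructions for an unlisted serious event: the three-level scale on the AE form, and CTCAE on the SAE form although the event is not in CTCAE.

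Safety and tolerability are the primary objective, and Section 12.2.2 says safety data are summarised descriptively, so any tabulation by severity is itself part of the safety result. Under Section 12.6 the DMC weighs the rate and severity of AEs and SAEs against the control arm after 6 treated patients. With so few patients, a single grade can influence how the data are read.

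**Working it through.** No figure in the protocol needs reproducing, and no error rate, effect size or sample size enters. The check is to apply each grading rule literally to the same event.

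**Step 1: which scale each place prescribes**

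| Place | Listed AE | Unlisted AE |
|---|---|---|
| Section 8.2.1.1 (AE form) | CTCAE v4.0 | mild, moderate, severe (1 to 3) |
| Section 8.2.1.2 (SAE form) | CTCAE v4.0 | CTCAE v4.0; no other rule given |
| Table 9 (content of AE form) | CTCAE v4.0 | CTCAE v4.0; no other rule given |
| Appendix 3 | CTCAE v4.0 | CTCAE v4.0; no other rule given |

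For listed events all four agree. For unlisted events the first row disagrees with the other three.

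**Step 2: the grade that reaches the AE form**

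The protocol equates grade 4 with life-threatening (Sections 8.1.1.2 and 8.1.1.3). It cites grade 5 in Appendix 2 without defining it. I assume that 5 means fatal.

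| Intensity of event | Listed AE | Unlisted AE |
|---|---|---|
| Mild | 1 | 1 |
| Moderate | 2 | 2 |
| Severe | 3 | 3 |
| Life-threatening | 4 | 3 |
| Fatal | 5 | 3 |

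The labels line up for the first three levels. If the two scales are read as one, the shortfall is 4 − 3 = 1 level for a life-threatening event and 5 − 3 = 2 levels for a fatal one.

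**Step 3: the same event on the SAE form**

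Appendix 2 makes an event serious if it is life-threatening or "Results in death", so every event in the last two rows also needs an SAE form. Section 8.2.1.2 does not say how to apply CTCAE to a term that CTCAE lacks. A site might grade by analogy and enter 4 or 5, in which case the two forms disagree. It might instead carry the 3 across, in which case the forms agree on the compressed grade. The protocol does not choose between these.

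**Step 4: what else records the event**

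- The SAE form is due within 24 hours of awareness (Section 8.2.1.2).
- The DMC reviews all SAEs (Section 8.2.5).
- A Death form records date and cause (Table 9).

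The compressed grade is therefore confined to the AE form and to summaries drawn from it.

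**Step 5: the appendix reference**

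Section 8.2.1.1 sends the reader to Appendix 4 for CTCAE. Appendix 4 describes the T-SPOT.TB test. The CTCAE reference is Appendix 3.

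**The case against.** The strongest reply is that nothing important goes unseen. A reader might infer from the ceiling at 3 that the worst unlisted events vanish from safety review. The documents do not support that: such events are SAEs by definition, are reported quickly on a separate form, and are all reviewed by the DMC, with deaths recorded once more. This part of the reply stands in full.

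A reader might also infer that the primary outcome as a whole rests on a mixed severity scale. It does not. Section 2.2 lists AEs and SAEs without the word severity and attaches severity only here: "Frequency, type and severity of infections". The severity element of the primary outcome is affected only if an infection is itself outside CTCAE.

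Three further replies have some force.

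- The protocol defines no table by grade and no grade threshold for the DMC, so how AE-form and SAE-form grades will be combined may be settled in the SAP. That is fair, but an analysis of AE-form grades cannot recover a level that the recording rule did not offer.
- Whether any life-threatening or fatal event falls outside CTCAE depends on a document the protocol only links to. That is also fair. The events the protocol describes above grade 3 have CTCAE grades already, so they do not show an affected case.
- Appendix 2 separates severity (intensity) from seriousness, so a three-level intensity scale could be defended on its own terms. It could, if it were kept apart. Here its values go on the same form as CTCAE grades, which carry life-threatening as a severity level.

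None of these replies removes the conflict between Section 8.2.1.1 and Section 8.2.1.2, Table 9 and Appendix 3.

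**Conclusion.** The point holds as a minor inconsistency in how severity is recorded. For an AE outside CTCAE, Section 8.2.1.1 prescribes a scale that three other places in the protocol do not recognise. Applied literally, an unlisted life-threatening or fatal event is a 3 on the AE form and may be something else on the SAE form. Summaries of severity taken from the AE form, including any the DMC uses under Section 12.6, would mix two scales and understate that event by one or two levels.

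The number of affected events cannot be derived from the protocol and may be zero. No hypothesis test, error rate or sample size changes. The conclusion assumes that sites follow Section 8.2.1.1 as written, that some event outside CTCAE can be worse than severe, and, for the two-level shortfall, that grade 5 means fatal. The correction is worth making because it costs almost nothing and safety is the primary objective.

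**What to change.** In Section 8.2.1.1, replace the three-level scale for unlisted AEs with five levels: 1 mild, 2 moderate, 3 severe, 4 life-threatening, 5 fatal. State that an event reported on both the AE form and the SAE form carries the same grade on each.

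Align the other places with this rule. Section 8.2.1.2, the AE entry in Table 9 and Appendix 3 should each say CTCAE version 4.0 where the event is listed and the five-level scale where it is not. In Section 8.2.1.1, change the CTCAE cross-reference from Appendix 4 to Appendix 3.

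The cost is a few sentences of text. If the AE form prints the three options, which cannot be checked because the form is not shown, it also needs two more. No additional visits, assessments or analyses are needed.

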8.2.1.2 Serious Adverse Events

For more detailed instructions on SAE reporting refer to the SAE Form Completion Guidelines contained in the relevant section of the ISF.

AEs defined as serious and which require reporting as an SAE should be reported on an SAE Form. When completing the form, the Investigator will be asked to define the causality and the severity of the AE which should be documented using the CTCAE version 4.0.

On becoming aware that a patient has experienced an SAE, the Investigator (or delegate) must complete, date and sign an SAE Form. The form should be faxed together with a SAE Fax Cover Sheet or emailed to the Trials Office using one of the numbers or the email address listed below as soon as possible and no later than 24 hrs after first becoming aware of the event:

To report an SAE by fax, fax the SAE Form with an SAE Fax Cover Sheet to:

[name] (primary number)

[name] (secondary number)

To report an SAE by email, email a scanned copy of the SAE Form to:

[contact]

On receipt the CDAID Trials Office will allocate each SAE a unique reference number. This number will either be transcribed onto the SAE Fax Cover Sheet which will then be faxed back to the site or emailed back to the site as proof of receipt which should be filed with the SAE form in the ISF. If confirmation of receipt is not received within 1 working day please contact the Trials Office. The SAE reference number should be quoted on all correspondence and follow-up reports regarding the SAE. The SAE Fax Cover Sheet completed by the CDAID Trials Office should be filed with the SAE Form in the ISF.

For SAE Forms completed by someone other than the Investigator, the Investigator will be required to countersign the original SAE Form to confirm agreement with the causality and severity assessments. This should

be done as soon as possible but can be done after returning to the Trial Office so as not to delay initial reporting. The form should then be kept in the ISF.

Investigators should also report SAEs to their own Trust in accordance with local practice.

8.2.1.3 Provision of follow-up information

Patients should be followed up until resolution or stabilisation of the event. Follow-up information should be provided on a new SAE Form (refer to the SAE Form Completion Guidelines for further information).

8.2.2 Trials Office

On receipt of an SAE Form seriousness and causality will be determined independently by a Clinical Coordinator. An SAE judged by the Investigator or Clinical Coordinator to have a reasonable causal relationship with the trial medication will be regarded as a Serious Adverse Reaction (SAR). The Clinical Coordinator will also assess all SARs for expectedness. If the event meets the definition of a SAR that is unexpected (i.e. is not defined in the Investigator Brochure) it will be classified as a Suspected Unexpected Serious Adverse Reaction (SUSAR).

8.2.3 Reporting to the Competent Authority and Research Ethics Committee

8.2.3.1 Suspected Unexpected Serious Adverse Reactions

The CDAID Trials Office will report a minimal data set of all individual events categorised as a fatal or life threatening SUSAR to the Medicines and Healthcare products Regulatory Agency (MHRA) and Research Ethics Committee (REC) within 7 days. Detailed follow-up information will be provided within an additional 8 days.

All other events categorised as SUSARs will be reported within 15 days.

Concurrently with the above, the trials office will report all such events to GSK's nominated safety representative (IMP provider).

8.2.3.2 Serious Adverse Reactions

The CDAID Trials Office will report details of all SARs (including SUSARs) to the MHRA and REC annually from the date of the Clinical Trial Authorisation, in the form of a Developmental Safety Update Report Adverse Events. Details of all AEs will be reported to the MHRA on request.

8.2.3.3 Adverse Events

Details of all AEs will be reported to the MHRA on request.

8.2.3.4 Other safety issues identified during the course of the trial

The MHRA and REC will be notified immediately if a significant safety issue is identified during the course of the trial.

8.2.4 Investigators

Details of all Unexpected and Related SAEs and any other safety issue which arises during the course of the trial will be reported to Principal Investigators. A copy of any such correspondence should be filed in the ISF.

8.2.5 Data Monitoring Committee

The independent Data Monitoring Committee (DMC) will review all SAEs.

8.2.6 Provider of the medicinal product

All SAEs that have a direct causal relationship *(related to study medication)* to the IMP *(as determined by the clinical coordinator)* will be reported to the provider (GSK) of the Investigational Medicinal Product (GSK1070806) within 24 hrs of evaluation by email or fax.

Nb: For the purposes of clinical evaluation or initial reviews of any SAE events will be assessed as if the participant received active medication (GSK1070806). If after this initial review the events was determined to be related to AND unexpected to the study drug (SUSAR) the patients allocation will be unblinded before expedited reporting a potential SUSAR event to the regulatory authorities and drug manufacturer (GSK)

8.2.7 Code Breaks / Unblinding of trial medication

Code Breaks / Unblinding for Medical Reasons Only (Site staff or other medical personnel located within the Hospital of admission)

When a patient taking part in the CDAID clinical trial is admitted to a hospital for an adverse event, careful consideration should be taken before a code break request is made. The patient should only be unblinded if the identity of the study drug is necessary for patient care. When considering if the patient should be unblinded, reference should be made to the current Investigator Brochure / Reference safety Information for GSK1070806 for drug contra-indications and known adverse event management. Where possible, prior discussion and approval for unblinding of study medication should be sought from one of the CDAID clinical coordinator(s) before a formal request is made. Contact details of the CDAID clinical coordinator(s) can be found in the Trial Personnel section of the protocol.

An unblinding service will be provided by the University Hospitals Birmingham NHS foundation Trust (UHBFT) – pharmacy department.

Details of this service can be found in the ISF and the pharmacy folder or on the individual patient cards. This will allow the local site Investigator, or other medically qualified person, to identify the trial medication (GSK1070806 or matched placebo) for an individual patient in an emergency, 24 hours a day and 365 days of the year. For further information regarding code break procedures please refer to the pharmacy file and the local site investigator file, or contact the CDAID Trial Coordinator.

8.2.7.1 Code Breaks for serious adverse event clinical evaluation by CDAID clinical coordinators (CDAID Trial office staff only)

When a serious adverse event is received by the central CDAID trial office (Birmingham UK) is deemed unexpected and possibly, probably or definitely related to the IMP and classified as a Suspected Unexpected Serious Adverse Reaction at first clinical evaluation by one of the CDAID Clinical Coordinator(s), the treatment will be subsequently be unblinded by a member of the study team. The event will then be clinically re-evaluated taking the treatment medication (GSK1070806 or Placebo) information into consideration. The resultant classification of the individual event will be either Unrelated Serious Adverse Event (for patients who received placebo), or Suspected Unexpected Serious Adverse Reaction (SUSAR) and will be reported as per the national clinical trial regulations of in the UK. Neither the patient nor the treating physician will be informed of the results of the code break and the patient will remain on study as per the clinical trial protocol. A record of the unblinding

CDAID

event will be stored along with the SAE and clinical evaluation in the main study Trial Master File. If it is subsequently deemed necessary to inform the treating clinician, trial site staff or patient of the treatment allocation (for patient safety reasons only), then the patient will come off study treatment and be followed up as per protocol. All code break requests for this study will be made via the University Hospitals Birmingham NHS foundation Trust (UHBFT) – pharmacy department.

